## 10.6. Study Drug Accountability

The Investigator is responsible for ensuring that an inventory is conducted upon receipt of the clinical supplies. The temperature recorder from the shipment will be deactivated and authorized study staff will verify that the temperature was maintained at -20°C or lower during transit. The clinical supplies shipment form should be completed, signed, and returned as directed. A copy must be maintained at the site for the Investigator's records.

The Investigator will keep a current record of the inventory, storage conditions and dispensing of all study drugs. This record will be made available to Santen (or designee) for the purpose of accounting for all clinical supplies. Any significant discrepancy and/or deficiency must be recorded with an explanation.

All supplies sent to the Investigator must be accounted for and in no case will study drugs be used in any unauthorized situation. It is the responsibility of the Investigator to ensure that any used and unused supplies are available to Santen (or designee) throughout the study.

### **10.7. Study Drug Handling and Disposal**

All investigational products including unused vials of study drug supplied by Santen will be returned to Santen or designee and be fully accounted for by the monitor with the help of the person responsible for dispensing the study drug. Accountability will be documented by use of drug accountability forms.

The used vials of study drug will be stored at the investigational site upon completion of accountability procedures and returned to Santen or designee, or destroyed at the site at the direction of Santen, after the trial is completed.

## **11. ASSESSMENT OF EFFICACY**

The long-term efficacy of DE-109 (440 µg) may be explored by VH.

## 12. ASSESSMENT OF SAFETY

### 12.1. Adverse Events, Serious Adverse Events and Events of Special Interest

#### 12.1.1. Definition of Adverse Events

An AE is any untoward medical occurrence in a subject administered a pharmaceutical product and which does not necessarily have a causal relationship with study drug. An AE therefore can be an unintended sign (including an abnormal laboratory finding), symptom, or disease temporally associated with the use of a medicinal (investigational) product, whether or not related to the medicinal (investigational) product.

In clinical studies, an undesirable medical condition occurring at any time, including baseline or wash-out period, may be recorded as an AE even if no study drug has been administered.

Any significant change in a subject's condition from baseline, regardless of causality, is to be considered an AE, unless the change is determined to be a continuation of a pre-existing condition that is documented in the subject's medical history. However, a clinically significant worsening in severity, intensity, or frequency of a pre-existing condition may indicate an AE.

Lack of efficacy of the study drug for the condition being investigated is not considered an AE unless a clinically significant change is assessed by the Investigator. In addition, any elective surgical procedure scheduled or planned prior to study entry is not considered an AE and the underlying diagnosis for which surgery is to be performed should be captured in the medical history as a pre-existing condition.

For this protocol, an AE is any *on-study* untoward medical occurrence (e.g. sign, symptom, disease, syndrome, intercurrent illness) that occurs in a study subject, regardless of the suspected cause and regardless of timing of DE-109 (440 µg) administration. An on-study AE can occur anytime after the date of informed consent through the last study visit. An AE will be considered as *treatment-emergent* if the AE occurred on or after the date of the first DE-109 (440 µg) treatment up to the last study visit. Treatment-emergent AEs are a subset of on-study AEs. Both on-study and treatment-emergent AEs will be reported.

#### 12.1.1.1. Assessment of Adverse Events

Investigators will seek information on AEs at each subject contact. Subjects should be asked using a general, non-direct question if there has been any change in their general health or well-being. Direct questioning and examination should then be performed as appropriate.

Severity of the AE should be assessed according to the following criteria:

**Mild:** Aware or unaware of event, but easily tolerated

**Moderate:** Discomfort enough to cause interference with usual activities

**Severe:** Incapacitating; unable to work or perform usual activity.

Regardless of severity, some AEs may also meet regulatory serious criteria. Refer to definitions and reporting of serious adverse events (SAEs) in Section 12.1.2.

An Investigator who is qualified in medicine must make the determination of relationship to the study drug for each AE (related or not related). The Investigator should decide whether, in his or her medical judgment, there is a reasonable possibility that the study drug caused the AE/SAE based on facts, evidence, science-based rationales, and clinical judgment. When assessing causality, the Investigator may consider the following information when determining the relationship to the study drug for each AE: mechanism of action, biologic plausibility, confounding risk factors (i.e., medical history, concomitant medications), temporal relationship, dechallenge/rechallenge, and lack of alternative explanation.

- The AE may be recorded as **Related** to study drug if there is a plausible temporal relationship between the onset of the AE and administration of the study drug, and the AE cannot be readily explained by the subject's clinical state, inter-current illness, or concomitant therapies; and/or the AE follows a known pattern of response to the study drug; and/or the AE abates or resolves upon discontinuation of the study drug or dose reduction and, if applicable, reappears upon re-challenge.
- Reporting the AE as **Not Related** to study drug may be considered if, for example, there is good evidence that the AE has an etiology other than the study drug (e.g., pre-existing medical condition, underlying disease, inter-current illness, or concomitant medication); and/or the AE has no plausible temporal relationship to administration of the study drug (e.g., cancer diagnosed 2 days after first dose of study drug).

#### 12.1.1.2. Reporting Adverse Events

AEs, whether spontaneously reported by the subject or noted by authorized study personnel, will be recorded in the subject's medical record and on the appropriate AE eCRF. Each recorded AE will be described by its duration (i.e., start and end dates), severity, regulatory seriousness criteria if applicable, suspected relationship to the study drug, and actions taken.

AEs that occur after any subject has provided written informed consent up to Month 12 must be recorded. If an adverse event is ongoing at the time of study exit, then the Investigator should perform reasonable follow-up efforts as necessary (e.g. telephone contact, post-study office visit) to determine the outcome of the event. To improve the quality and precision of acquired AE data, Investigators should observe the following guidelines:

- Whenever possible, use recognized medical terms when recording. Do not use colloquialisms and/or abbreviations.
- If known, record the diagnosis (i.e., disease or syndrome) rather than component signs and symptoms (e.g., record congestive heart failure rather than dyspnea, rales, and cyanosis). However, other events that are considered unrelated to an encountered syndrome or disease should be recorded as individual AEs (e.g., if congestive heart failure and severe headache are observed at the same time and are clinically unrelated, each event should be recorded as an individual AE).
- AEs occurring secondary to other events (e.g., sequelae) should be identified by the primary cause. A primary AE, if clearly identifiable, generally represents the most accurate clinical term. If a primary AE is recorded, events occurring secondary to the primary event should be described in the narrative description of the case.

For example:

The subject developed orthostatic hypotension and subsequently fainted and fell to the floor wherein she experienced a head trauma and neck pain.

The primary AE in this example is orthostatic hypotension.

- For intermittent events (e.g., intermittent headache) and events that occur with each instillation (e.g., eyes burn for 5 minutes after every dose), the event start date should be recorded as the date the subject first started to experience the event. The end date should reflect when the last occurrence resolved or stopped. For example, if a subject had an intermittent headache from 14 MAY 2014 until 21 MAY 2014 and each individual headache lasts 3 hours a day, then the date of resolution is 21 MAY 2014 (not 14 MAY 2014).
- For intermittent events, record the maximum severity of the individual events. For example, if a subject complains of intermittent headaches for one week and the severity of each headache ranges from mild to moderate, then the severity would be moderate.
- If an event occurs with each instillation (e.g., eyes burn mild to moderate for 5 minutes after every dose), record the maximum severity of the individual incident. In the example above, the severity is moderate.

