**Investigational product, dosage and mode of administration:**

Investigational product: DE-109 injectable solution, 440 µg.

Subjects will be treated at the discretion of the Investigator, but no more frequently than every 60 days.

Route of Administration: 20 $\mu$ L intravitreal injection in the study eye.
Duration of the Study: 12 months or commercial availability of DE-109, whichever comes first.
Criteria for Evaluation:
Safety: The long-term safety of DE-109 440 $\mu$ g will be assessed based on adverse events, visual acuity, intraocular pressure, indirect ophthalmoscopy variables, vitreous haze and the use of rescue therapy.
Efficacy: Efficacy is not the main objective of this extension study. The long-term efficacy of DE-109 440 $\mu$ g may be explored by vitreous haze.
Safety Parameters: 

• Adverse event incidence rate

• Change in best-corrected visual acuity

• Change in intraocular pressure

• Change in indirect ophthalmoscopy findings

• Change in vitreous haze

• Proportion of safety subjects who were rescued

Statistical Methods: 
This extension study is implemented to provide subjects with access to DE-109 to benefit those who have received at least two injections of DE-109 during the first 5-month treatment of the SAKURA development program and to evaluate the long-term safety of DE-109 440 <math>\mu</math>g in subjects with non-infectious uveitis of the posterior segment of the eye.
 
No statistical hypotheses will be tested in this study.
 
The safety data will be summarized descriptively. The Safety population will include all enrolled subjects with any safety data collected during the study, whether or not they ever receive any injection of DE-109 (440 <math>\mu</math>g). It will be the analysis population for safety summaries.
 
The formal definition of rescue therapy will be adequately documented based on clinical data review of this extension study prior to database lock.

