### 7.5.3. Post-Baseline PRN Treatment Visit

The subject may receive DE-109 treatments at the discretion of the Investigator, but no more frequently than every 60 days. If a subject receives treatment with DE-109 between scheduled study assessments, the following procedures will be performed:

- Update medications
- If the subject is a woman of child-bearing potential, perform a urine pregnancy test
- BCVA
- IOP
- Indirect ophthalmoscopy
- VH
- AE.
- If in the judgment of the Investigator, the subject needs DE-109 treatment, it has been at least 60 days since the last treatment, and the results of the urine pregnancy test were negative (for women of child-bearing potential), perform the study drug administration procedures as described in Section 10.4 and Section 10.5.
- The following assessments must be performed after the administration of study drug:
  - Indirect ophthalmoscopy within 30 minutes following injection
  - IOP 40 ( $\pm 10$ ) minutes following injection
  - AEs.

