### 8.1. Inclusion criteria

At Day 1, a subject from the SAKURA program must meet all of the following inclusion criteria:

1. Have a subject number from participation in the SAKURA program
2. Exited the SAKURA program under Amendment 05
3. Have received at least two injections of DE-109 in the first five months of the SAKURA program
4. Received clinical benefit from treatment with DE-109 as determined by the Investigator
5. Female participants of childbearing potential must not be pregnant or breast-feeding, have a negative pregnancy test at screening and must be willing to undergo pregnancy tests throughout the study
6. Both female participants of childbearing potential and male participants able to father children must have (or have a partner who has) had a hysterectomy or vasectomy, must abstain from intercourse or must agree to practice acceptable methods of contraception throughout the course of the study.
7. Ability to give informed consent and attend all study visits

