#### **7.6. Treatment Exposure**

The extent of exposure to DE-109 (440 µg) in the SPRING study will be assessed by the number of DE-109 injections (0, 1, 2, 3, 4, 5, or 6) together with days on treatment (<60, ≥60 and <120, ≥120 and <180, ≥180 and <240, ≥240 and <300, or ≥300).

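### An eye-drop rule for recurring adverse events, applied to injections at least 60 days apart, merges separate post-injection reactions into one record and can date it before SPRING consent

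*Protocol*

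**What the plan says.** Protocol 12.1.1.2 (Reporting Adverse Events) gives sites guidelines on how to record AEs. One covers intermittent events together with "events that occur with each instillation (e.g., eyes burn for 5 minutes after every dose". For both kinds, "the event start date should be recorded as the date the subject first started to experience the event", and "The end date should reflect when the last occurrence resolved or stopped". A companion guideline asks for the maximum severity over the individual incidents. One recurring reaction therefore has one start date, one end date and one severity.

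The product is not instilled. The synopsis gives the route as "intravitreal injection in the study eye", and Protocol 7.5.3 allows treatment "no more frequently than every 60 days". SAP 7.6 tabulates exposure by "number of DE-109 injections (0, 1, 2, 3, 4, 5, or 6").

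All subjects come from an earlier trial of the same drug. Protocol 8.1 requires them to "Have received at least two injections of DE-109 in the first five months of the SAKURA program".

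Protocol 12.1.1 states: "An on-study AE can occur anytime after the date of informed consent through the last study visit". SAP 4.4.1 repeats this and defines a treatment-emergent AE as one occurring on or after the first 440 µg injection in SPRING. SAP 8.1 bases the AE analysis on on-study AEs, flags treatment-emergence in the listings, and counts a subject once per system organ class or preferred term.

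**The concern.** With daily drops, folding a brief recurring symptom into one record is sensible: doses are close together and the episodes form one continuous experience. With injections two months or more apart, each reaction is a separate event that follows its own exposure and resolves before the next.

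The study's only objective is the long-term safety of repeated as-needed injections. Table 3 has AEs elicited before and after each injection, so the information is collected per injection and the recording rule then discards that detail. Protocol 12.1.1.1 bases causality partly on the time between administration and onset and on reappearance at re-challenge. A merged record keeps only the first onset, so it cannot show that the reaction came back, after which injections, or whether it became milder or more severe. Injection-procedure-related AEs have their own tables and listings (Protocol 14.6, SAP 8.1), and the listings are where this loss would show.

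There is a second, less certain problem. A reaction that really follows every dose may well have begun in SAKURA. The start-date rule does not limit first experience to this study, so a site following it literally could enter a date before SPRING consent. That date would conflict with the on-study and treatment-emergent definitions, and neither document says how to classify such a record.

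**Working it through.** **Inputs.** Minimum interval of 60 days (Protocol 7.5.3). First possible injection on Day 1 (Protocol Table 3). Month 12 at Day 360 ± 14 (Protocol 7.5.2), which is Day 346 to Day 374. Injection categories 0 to 6 (SAP 7.6). A 5-minute reaction as the protocol's own example (12.1.1.2). Enrolment of 60 subjects (SAP 3.3).

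**Number of injections.** At the minimum spacing, injection days are 1 + 60 × (k − 1): Days 1, 61, 121, 181, 241 and 301. That is six before a Month 12 visit on Day 346 or Day 360, which matches the top category in SAP 7.6. A Month 12 visit at the late edge, Day 374, would leave room for a seventh on Day 361.

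**Span of the merged record.** Assume that the reaction follows each of k injections and resolves the same day. The record then spans (k − 1) × 60 + 1 days.

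| Injections with reaction | Correct records | Records under the rule | Span of merged record | Symptom time at 5 minutes each |
|---|---|---|---|---|
| 2 | 2 | 1 | 61 days | 10 minutes |
| 3 | 3 | 1 | 121 days | 15 minutes |
| 6 | 6 | 1 | 301 days | 30 minutes |

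If each reaction instead fills one day, six of them make 6 days, against a recorded 301 days: 301 / 6 ≈ 50 times too long. Six is the extreme case in a PRN study, but two reactions already give a 61-day record.

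**Effect on planned tables.** A subject with six records of one preferred term contributes 1 to the numerator out of 60. A subject with one merged record also contributes 1. The change in n (%) is 1 − 1 = 0. Tables by maximum severity do not move either, because the merged record carries the maximum. Record counts, onset, duration and the link to an injection do change.

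**SAKURA route, texts side by side.**
- The start-date rule (Protocol 12.1.1.2) refers to first experience, with no limit to this study.
- The on-study definition (Protocol 12.1.1, SAP 4.4.1) refers to occurrence between consent and last visit.
- The recording duty (Protocol 12.1.1.2) covers AEs that occur after consent up to Month 12.
- SAP Table 4 imputes partial onset dates but does not derive on-study status from them.

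A recurrence after a SPRING injection is therefore an on-study AE by definition, yet its record may carry a start date before consent. The texts leave that conflict open. They give no rate of reactions and no share that began in SAKURA, so no effect on incidence can be calculated.

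**The case against.** The strongest reply has four parts.

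1. **An injection is not an instillation.** The only dated example is an intermittent headache lasting 8 days (14 to 21 May 2014), and nothing expressly tells sites to join resolved events two months apart. This is fair as far as it goes. But the guideline's own gloss speaks of every dose, and in this study the only dose is an injection. Sites that look for a rule on dose-related reactions will find this one.

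2. **The planned analysis is largely immune.** No AE summary per injection and no duration summary is specified. Acute effects are also measured outside the AE form: IOP and ophthalmoscopy before and after injection, summarised under SAP 8.4 and 8.5. This stands for the tables, and it limits the point to listings, onset, duration and causality. It does not cover symptoms that neither examination captures.

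3. **Nothing removes reactions first seen in SAKURA.** A reader might infer that these reactions drop out of the on-study set, so that reported incidence falls among the subjects who react most often. The documents do not support this. It requires reading first experience as reaching back into an earlier trial, and then filtering AEs by recorded start date. Neither document takes the second step, and both define AEs by occurrence after consent. The exclusion in Protocol 12.1.1 for continuation of a documented pre-existing condition could tempt a site to leave out a known reaction, but the text does not direct that. What stands is an ambiguity.

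4. **The change is late.** SAP 3.3 says that enrolment was complete by 18 November 2016, so some records may already be merged and would need queries to sites. This is correct, and it is part of the cost.

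**Conclusion.** The point holds as a defect in recording. Read as applying to injections, the rule turns up to six separate reactions into one record spanning up to 301 days at minimum spacing, or 61 days for two. AE onset and duration in the listings are then wrong, recurrence on re-exposure is hidden, and reactions cannot be tied to or counted by injection. The effect on planned subject-level n (%) and on maximum severity is zero.

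A start date before consent is a credible further risk, because prior DE-109 exposure is universal and the rule has no study boundary. Its size is unknown. A general downward bias in incidence is not established.

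This rests on three assumptions: that sites read dose as injection; that each reaction resolves before the next injection; and that the same guidelines apply under US Amendment 01. The SAP follows that amendment, but the protocol supplied lacks the Month 2 to 10 visits that the SAP describes for it.

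**What to change.** - **Protocol 12.1.1.2 or eCRF guidelines:** replace the instillation wording. Each reaction after a separate DE-109 injection is a new AE record with its own start date, end date and severity.
- **Intermittent events:** limit the existing rule to recurrences between two consecutive injections.
- **Link to SAKURA:** state that a reaction recurring after a SPRING injection is on-study and carries its SPRING onset date, even if the subject had it in SAKURA.
- **SAP 4.4.1:** add one line on how an AE with a start date before SPRING consent is classified as on-study and treatment-emergent.

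Table formats stay as they are. The cost is wording, more AE records per subject who reacts repeatedly, and site queries to split any records already merged. Where a site cannot recover the separate dates, the study report should say so.

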### **12.1.2. Serious Adverse Events**

SAEs are defined as any findings that suggest a significant hazard, contraindication, side effect, or precaution. Any adverse event is considered a serious adverse event if it results in any of the following outcomes:

- Death
- Life threatening:

A life-threatening event is any event that places the subject at immediate risk of death from the event as it occurred; it does not refer to an event that hypothetically might have caused death if it were more severe.

- In-subject hospitalization and/or prolonged hospitalization
- A persistent or significant disability/incapacity
- A congenital anomaly/birth defect
- Sight threatening event:

A sight-threatening event is any event that places the subject at immediate risk of permanently losing vision in either eye as a direct result of the event (See Section [12.1.3](#)).

- Other medically significant events:

Other medically significant events are events that may not result in death, be life-threatening, or require hospitalization but may be considered a serious adverse drug experience when, based upon appropriate medical judgment, they may jeopardize the subject and may require medical or surgical intervention to prevent one of the outcomes listed above.

